4.4.2.5.7 AEs of Special Interest (AESIs)

An AESI is an event for which ongoing monitoring and rapid communication by the Investigator to the Sponsor must be done. Such an event might warrant further investigation to characterize and understand it. Depending on the nature of the event, rapid communication by the study Sponsor to other parties (e.g., regulators) might also be warranted.

Because of their medical importance and to ensure expedited communication to the Sponsor, these AESIs are to be considered and collected as SAEs and reported to the Sponsor.

AESIs were to be collected throughout the study. The AESIs that will be retrieved for analysis in this trial are presented in [Section 4.3.2.6](#).

4.4.2.5.8 Medically Attended AE (MAAE)

An MAAE is a new onset or a worsening of a condition that prompts the subject to seek unplanned medical advice at a physician's office or emergency department. A physician contact made over the phone or by email will be considered a physician office visit for the purpose of MAAE collection. This definition excludes pre-planned medical office visits for routine medical care, as well as follow-up visits of chronic conditions with an onset prior to entry in the study. An AE discovered during a planned routine visit (e.g., upper respiratory tract infection, otitis) will be collected as an MAAE.

4.4.3 Derived Other Variables

4.4.3.1 Time since Primary Vaccination in Either MET44 or MET49

Time in years since primed vaccines is computed as follows: (Date of Vaccination in MEQ00066 – Date of Vaccination in MET44, MET49 + 1) / 365.25

4.4.3.2 Age for Demographics

The age of a subject in the study is the calendar age as defined in the protocol.

4.4.3.3 Age Subgroup for Demographics

Age subgroups for Groups 1 and 2 are as follows:

- 59 through 64 years
- ≥ 65 years

4.4.3.4 Race for Subgroup Analyses

Race for subgroup analyses will be categorized as:

- White
- Asian
- Black or African American
- Other

Note: The original race categories collected in CRF will still be used for demographics analyses. The American Indian or Alaska Native, Native Hawaiian or Other Pacific Islander, Mixed origin, Not Reported and Unknown will be classified into “Other” stratum for subgroup analysis purposes only.

4.4.3.5 Duration of a Subject in the Trial

The duration of a subject in the study is computed as follows:

Maximum (date of last visit, date of termination) – (date of visit 1 of that subject) +1.

The calculation should be conducted for:

- Groups 1 and 2 at the end of stage I
- Groups 5 and 6 at the end of stage I
- Groups 3 and 4 at the end of stage II

4.4.3.6 Duration of the Study

The duration of the study is computed in days as follows:

Maximum of all subjects (date of last visit, date of termination) – minimum for all subjects (date of Visit 1) +1.

The calculation should be conducted for:

- Groups 1 and 2 at the end of stage I
- Groups 5 and 6 at the end of stage I
- Groups 3 and 4 at the end of stage II

4.4.3.7 Protocol-Prohibited Therapy, Medications or Vaccines

In general, the “prohibited” variable is not derived. All concomitant medications are reviewed by the clinical team and the value of the “prohibited” variable is determined before database lock by the clinical team.

Only two categories of reportable medications will be considered for protocol-prohibited/restricted therapy, medications or vaccines:

Category 2:

- Influenza vaccines administered within 14 days before or after vaccination with the study vaccine
- Other vaccines not included as study vaccines (e.g., oral poliovirus, yellow fever, Japanese encephalitis, or other routine/non-routine vaccines not described in the protocol) within the 28 days (4 weeks) preceding or after vaccination with the study vaccine
- Immune globulins, blood or blood-derived products and immunosuppressive therapy, as described in the protocol.

Category 3:

- Antibiotics that the subject received within the 72 hours preceding each visit for blood sampling related to assessment of the study vaccine

Receipt of the above protocol-prohibited therapy, medications, or vaccines at or around the time of specific visits may impact safety and/or immunogenicity analyses.

5 Statistical Methods and Determination of Sample Size

The statistical analyses will be performed under the responsibility of the Sponsor's Biostatistics platform using SAS® Version 9.4 software or later.

The results of the statistical analysis will be available in the final clinical study report (CSR).

For descriptive purposes, the following statistics in [Table 5.1](#) will be presented. The confidence intervals (CI) for the single proportions will be calculated using the exact binomial method (Clopper-Pearson method, quoted by Newcombe [\(10\)](#), ie, using the inverse of the beta integral with SAS®).

For immunogenicity results, assuming that Log10 transformation of the titers' data follow a normal distribution, at first, the mean and the 95% CI will be calculated on Log10 (titers data) using the usual calculation for normal distribution (using Student's t distribution with n-1 degree of freedom), then antilog transformations will be applied to the results of calculations, in order to provide GMs and their 95% CI.

Table 5.1: Descriptive Statistics Produced

Baseline characteristics and follow-up description	Categorical data	Number of subjects. Percentage of subjects.
	Continuous data	Mean, standard deviation, quartiles, minimum, and maximum.
Clinical safety results	Categorical data	Solicited: Number and percentage (95% CIs) of subjects. Unsolicited: Number and percentage (95% CIs) of subjects, and number of events.
Immunogenicity results	Categorical data (seroresponse, ≥ 4-fold rise, cutoff)	Number and percentage (95% CIs) of subjects.
	Continuous data (titer / data)	Log10: Mean and standard deviation. Anti-Log10 (work on Log10 distribution, and anti-Log10 applied): Geometric mean, 95% CI of the GM, quartiles, minimum, and maximum. Graphical representation by reverse cumulative distribution curves (RCDCs).

5.1 Statistical Methods

5.1.1 Hypotheses and Statistical Methods for Primary Objective

5.1.1.1 Hypotheses

Thirty days after the administration of MenACYW conjugate vaccine, the sufficiency of the vaccine seroresponse as assessed by the percentages of subjects who achieve an hSBA vaccine seroresponse* for meningococcal serogroups A, C, W, and Y, in Group 1 will be tested.

Vaccine seroresponse will be considered sufficient if the lower limit of the 1-sided 97.5% confidence interval (CI) for the percentage of subjects with an hSBA vaccine seroresponse against serogroups A, C, W and Y is greater than 40%.

This is equivalent to testing $H_0: p \leq 0.40$ against $H_1: p > 0.40$, where p is the observed proportion of subjects with hSBA vaccine seroresponse against serogroups A, C, W and Y. The 1-sided 97.5% CI for the single proportion will be calculated using the exact method (Clopper-Pearson method).

*hSBA vaccine seroresponse for serogroups A, C, W, and Y is defined as:

- For a subject with a pre-vaccination titer $< 1:8$, the post-vaccination titer must be $\geq 1:16$.
- For a subject with a pre-vaccination titer $\geq 1:8$, the post-vaccination titer must be at least 4-fold greater than the pre-vaccination titer.

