2.2 Secondary Objectives

Secondary Objective 1

- To demonstrate sufficiency of the vaccine seroresponse to meningococcal serogroups A, C, W, and Y following administration of a single dose of MenACYW conjugate vaccine to Group 2 subjects (who received primary vaccination with MenACYW conjugate vaccine \geq 3 years earlier at \geq 56 years of age in Study MET49).

Secondary Objective 2

- To describe vaccine seroresponse rates with respect to serogroups A, C, W, and Y in serum specimens collected 6 (window, 5–7) days post-vaccination in approximately 60 subjects from Group 1 (Menomune-primed) and approximately 60 subjects from Group 2 (MenACYW conjugate vaccine-primed).

Secondary Objective 3

- To describe antibody persistence \geq 3 years after primary vaccination with Menomune vaccine or MenACYW conjugate vaccine for subjects from all groups.

The endpoints for the secondary objectives are presented in [Section 4.2.1.1](#).

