4.3 Observational Endpoints and Assessment Methods

4.3.1 Immunogenicity

4.3.1.1 Immunogenicity Endpoints

Antibody titers (hSBA and rSBA) will be measured for each meningococcal serogroup for the following groups of subjects:

- For all subjects on Day 0
- For a subset of subjects in Groups 1 and 2, on Day 6 (window, Days 5–7) following vaccination
- For subjects in Group 3 and 4, on Day 0 (Visit 1) + 2 years
- For all subjects who receive a single dose of MenACYW conjugate vaccine, 30 (window, + 14) days following vaccination

Tetanus toxoid is contained in the investigational vaccine as a carrier protein. Therefore, BLs will also be tested to assess:

- Antibody concentrations against tetanus toxoid at Day 0 (all groups), 2 years after enrollment (Groups 3 and 4), and 30 (window, + 14) days after the administration of a single dose of MenACYW conjugate vaccine in Study MEQ00066 (Groups 1-4)

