5.1.2 Hypotheses and Statistical Methods for Secondary Objectives

5.1.2.1 Hypotheses

5.1.2.1.1 Secondary Objective 1

Thirty days after the administration of MenACYW conjugate vaccine, the sufficiency of the vaccine seroresponse, as assessed by the percentages of subjects who achieve an hSBA vaccine seroresponse* for meningococcal serogroups A, C, W, and Y, in Group 2 will be tested.

Vaccine seroresponse will be considered sufficient if the lower limit of the 1-sided 97.5% interval (CI) for the percentage of subjects with an hSBA seroresponse against serogroups A, C, W and Y is greater than 40%.

This is equivalent to testing $H_0: p \leq 0.40$ against $H_1: p > 0.40$, where p is the observed proportion of subjects with hSBA seroresponse against serogroups A, C, W and Y. The 1-sided 97.5% CI for the single proportion will be calculated using the exact method (Clopper-Pearson method).

*hSBA vaccine seroresponse for serogroups A, C, W, and Y is defined as:

- For a subject with a pre-vaccination titer $< 1:8$, the post-vaccination titer must be $\geq 1:16$.
- For a subject with a pre-vaccination titer $\geq 1:8$, the post-vaccination titer must be at least 4-fold greater than the pre-vaccination titer.

5.1.2.1.2 Secondary Objective 2

No hypotheses will be tested.

5.1.2.1.3 Secondary Objective 3

No hypotheses will be tested.

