5.1.2.2 Statistical Methods

5.1.2.2.1 Secondary Objective 1

The CIs for the single proportions will be calculated using the exact binomial method (Clopper-Pearson method, quoted by Newcombe (10), i.e., using the inverse of the beta integral with SAS[®]).

5.1.2.2.2 Secondary Objective 2

The proportions of subjects in a planned nonrandom subset (approximately 60 subjects from Group 1 and approximately 60 subjects from Group 2) with vaccine seroresponse for meningococcal serogroups A, C, W, and Y at 6 (window, 5–7) days following vaccination will be determined; 95% CIs of point estimates will be calculated assuming proportions follow a binomial distribution using the Exact method.

5.1.2.2.3 Secondary Objective 3

For GMTs, the 95% CIs of point estimates will be calculated using the normal approximation assuming antibody titers/concentrations are log normally distributed. For proportions, 95% CIs of point estimates will be calculated assuming proportions follow a binomial distribution using the Exact method.

Categorical variables will be summarized and presented by frequency counts, proportion percentages, and confidence intervals (CIs). The 95% CIs of point estimates will be calculated using the normal approximation for quantitative data and the exact binomial distribution (Clopper-Pearson method) for percentages (6).

RCDC figures and kinetic curves will be provided for the antibody titers against meningococcal serogroups contained in MenACYW conjugate vaccine.

Descriptive analyses on A, C, W, and Y serogroups will include:

- hSBA and rSBA GMTs and corresponding 95% CIs
- hSBA and rSBA titer distribution and RCDCs

- Percentages of subjects with hSBA titer $\geq 1:4$ and $\geq 1:8$ and corresponding 95% CIs
- Percentages of subjects with rSBA titer $\geq 1:8$ and $\geq 1:128$ and corresponding 95% CIs

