5.5 Determination of Sample Size and Power Calculation

A total of 560 subjects are planned to be enrolled:

- Group 1 (subjects who received Menomune vaccine in Study MET49) will receive a single dose of MenACYW conjugate vaccine at enrollment in Study MEQ00066: n=180
- Group 2 (subjects who received MenACYW conjugate vaccine in Study MET49) will receive a single dose of MenACYW conjugate vaccine at enrollment in Study MEQ00066: n=180
- Group 3 (subjects who received Menomune vaccine in Study MET49) will receive a single dose of MenACYW conjugate vaccine 2 years after enrollment in Study MEQ00066: n=40
- Group 4 (subjects who received MenACYW conjugate vaccine in Study MET49) will receive a single dose of MenACYW conjugate vaccine 2 years after enrollment in Study MEQ00066: n=40
- Group 5 (subjects who previously received Menomune vaccine in Study MET44): n=60
- Group 6 (subjects who previously received MenACYW conjugate vaccine in Study MET44): n=60

For the Primary Objective and Secondary Objective 1: For Group 1 and Group 2, a sample size of 120 achieves at least 90.0% power to detect that the lower bound of the one-sided 97.5% CI is greater than 0.40 (proportion under the null hypothesis) using a 1-sided exact test with a significance level (alpha) of 0.025.

For all other groups (i.e, Groups 3–6), descriptive statistics will be calculated and presented in this study; hence, no sample size or study power was calculated for these groups.

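### Do the seroresponse hypotheses, written with one observed p for A, C, W and Y, leave the success rule open?

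*SAP*

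**What the plan says.** For the primary objective (Group 1), SAP 5.1.1.1 opens with the plural, "as assessed by the percentages of subjects who achieve an hSBA vaccine seroresponse". It then gives one null and one alternative at 0.40, "where p is the observed proportion of subjects with hSBA vaccine seroresponse against serogroups A, C, W and Y", and continues: "The 1-sided 97.5% CI for the single proportion will be calculated using the exact method". Success means that the lower limit exceeds 40%.

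SAP 5.1.2.1.1 repeats the structure for Group 2, "where p is the observed proportion of subjects with hSBA seroresponse against serogroups A, C, W and Y". The matching methods text in 5.1.2.2.1 uses the plural: "The CIs for the single proportions will be calculated using the exact binomial method".

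The Group 2 objective in 2.2 is worded "To demonstrate sufficiency of the vaccine seroresponse to meningococcal serogroups A, C, W, and Y", and the Group 1 objective in 2.1 takes the same form. On sample size, 5.5 says that "a sample size of 120 achieves at least 90.0% power to detect that the lower bound of the one-sided 97.5% CI" exceeds 0.40, and it names no assumed response rate.

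**The concern.** Two things look wrong. First, a null hypothesis about an observed proportion is not a hypothesis, because the observed value is known once the data are in. Second, four serogroups share one p and one interval. The words *each* and *all four* do not appear in the decision rule, and the power statement speaks of one lower bound, so it does not settle the matter.

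If the text really left the rule open, three tests would be possible:

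- **All four serogroup tests must pass.** Type I error is at most 0.025.
- **Any one suffices.** Type I error could reach 1 − 0.975^4 = 9.6% if the serogroups were independent.
- **p is the share responding to all four serogroups.** With a true rate of 70% in each serogroup and independent responses, that share is 0.7^4 = 0.240, and a test against 0.40 would almost never succeed although each serogroup passes easily.

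A result in which only some serogroups pass would also have no written consequence, so a claim might be shaped after the data are seen.

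**Working it through.** **1. The plan's own figure.** Inputs from 5.1.1.1 and 5.5: null 0.40, one-sided exact test at 0.025, 120 subjects as the power basis, 180 planned in each of Groups 1 and 2. The threshold is the smallest r with P(X ≥ r | n, 0.40) ≤ 0.025. The lower limit is the 0.025 quantile of Beta(r, n − r + 1).

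| n | Threshold | Lower limit there | Lower limit one below | Exact size |
|---|---|---|---|---|
| 120 | 60 | 0.4074 | 0.3993 | 0.0167 |
| 180 | 86 | 0.4029 | 0.3975 | 0.0206 |

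The 90% power cannot be reproduced as stated, because 5.5 gives no true rate. Solving P(X ≥ 60 | 120, p) = 0.90 gives p = 0.554 for one test. The confidence-limit rule and the exact test agree, so the decision is computed from the limit. The word *observed* never enters a calculation.

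**2. Which proportion is meant?** Setting the sections side by side:

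- 4.4.1.2.1 and the footnotes in 5.1.1.1 and 5.1.2.1.1 define seroresponse from one pre-vaccination and one post-vaccination titer. Nothing combines serogroups into a subject-level outcome.
- 4.3.1.1 says that titers "will be measured for each meningococcal serogroup".
- 5.1.1.1 opens with percentages and 5.1.2.2.1 refers to proportions, both plural.
- 5.2.1.1 admits a subject to the Day 30 full analysis set with a valid result for at least one serogroup. 5.2.1.2.1 drops a subject for lack of a valid result only when every antigen is missing. 5.3.2 imputes nothing. A subject with three responses and one missing titer has no defined all-four outcome, and the plan supplies no rule for one. A serogroup-by-serogroup analysis needs no such rule.

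The all-responder composite therefore cannot be carried out as the plan stands, while the per-serogroup analysis can.

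**3. Which combination rule?** Objectives 2.1 and 2.2 and the criterion in 5.1.1.1 join A, C, W and Y with *and*. Nothing supports an any-one rule. If all four must pass and some serogroup has a true rate at or below 0.40, then

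P(all four pass) ≤ P(that serogroup passes) ≤ 0.0167 at n = 120, or 0.0206 at n = 180.

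The level holds whatever the correlation among serogroups.

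**4. How often would only some serogroups pass?** The assumptions here are an equal true rate in all four serogroups and independence. P(some but not all) = 1 − w^4 − (1 − w)^4, where w is the power of one test.

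| True rate | n | w | All four pass (w^4) | Some but not all |
|---|---|---|---|---|
| 55% | 120 | 0.8833 | 0.609 | 0.391 |
| 55% | 180 | 0.9782 | 0.916 | 0.084 |
| 60% | 120 | 0.9895 | 0.959 | 0.041 |
| 60% | 180 | 0.9996 | 0.999 | 0.001 |

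With latent correlation between 0 and 0.7, the simulated 55% figures run from 28% to 39% at n = 120 and from 7% to 9% at n = 180. Under a conjunctive objective each of these outcomes has one consequence: the objective is not met, and the four estimates are reported with their intervals.

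**The case for a change.** The strongest case for a change is that the confirmatory criterion of a primary objective should be written out, not inferred. Section 5.1.1.1 is headed as the place for the hypotheses and sets them out in full, so the looseness cannot simply be put down to the protocol. The figures on this side are correct. At a 70% rate per serogroup and n = 120, the literal composite test would succeed between 0% and 40% of the time for latent correlation 0 to 0.7, against about 100% for four separate tests. At a 55% rate and n = 120, a partial result is not rare.

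What stands is the description: *observed* is the wrong word, and this SAP contains no explicit all-four sentence. The consequences do not stand. The composite figures measure a test that the definitions and analysis sets do not support. The partial-result figures need both a rate only 15 points above the null and the smaller n; at 180 subjects and a 60% rate the chance is about 0.1%. Even where a partial result occurs, an objective naming A, C, W and Y is not met by three of them.

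Two side issues also fall away. Requiring all four at n = 120 raises the rate needed for 90% power from 0.554 to 0.584 under independence, but 5.5 states no rate that this contradicts, and at 180 subjects the joint figure is 0.547. Testing Secondary Objective 1 with no stated order relative to the primary gives up to 1 − 0.975^2 = 4.9% nominal error over the two objectives. The SAP makes no claim to control error across them, so this is a trade-off and not an inconsistency.

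**Conclusion.** The hypotheses are loosely worded, and no change to the plan follows. *Observed* is a clerical slip with no numerical effect, since the Clopper-Pearson limit decides. The missing serogroup-by-serogroup sentence is a gap that the plan's own definitions, analysis sets and conjunctive objective fill in only one workable way: four lower limits per group, all above 40%, with type I error at or below 0.025. Writing that down would leave every interval, error rate and conclusion as it is.

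This rests on reading the objective's *and* in its ordinary sense and on the SAP alone. The protocol was not available and may state the rule. The rates and correlations used above are assumptions, because the SAP gives none, but the conclusion does not depend on them: the error bound in step 3 holds for any rates and any correlation.

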5.1.1.2 Statistical Methods

The CI for the single proportion was calculated using the exact binomial method (Clopper-Pearson method, quoted by Newcombe (10), i.e., using the inverse of the beta integral with SAS®).

5.1.2 Hypotheses and Statistical Methods for Secondary Objectives

5.1.2.1 Hypotheses

5.1.2.1.1 Secondary Objective 1

Thirty days after the administration of MenACYW conjugate vaccine, the sufficiency of the vaccine seroresponse, as assessed by the percentages of subjects who achieve an hSBA vaccine seroresponse* for meningococcal serogroups A, C, W, and Y, in Group 2 will be tested.

Vaccine seroresponse will be considered sufficient if the lower limit of the 1-sided 97.5% interval (CI) for the percentage of subjects with an hSBA seroresponse against serogroups A, C, W and Y is greater than 40%.

This is equivalent to testing $H_0: p \leq 0.40$ against $H_1: p > 0.40$, where p is the observed proportion of subjects with hSBA seroresponse against serogroups A, C, W and Y. The 1-sided 97.5% CI for the single proportion will be calculated using the exact method (Clopper-Pearson method).

*hSBA vaccine seroresponse for serogroups A, C, W, and Y is defined as:

- For a subject with a pre-vaccination titer $< 1:8$, the post-vaccination titer must be $\geq 1:16$.
- For a subject with a pre-vaccination titer $\geq 1:8$, the post-vaccination titer must be at least 4-fold greater than the pre-vaccination titer.

5.1.2.1.2 Secondary Objective 2

No hypotheses will be tested.

5.1.2.1.3 Secondary Objective 3

No hypotheses will be tested.

5.1.2.2 Statistical Methods

5.1.2.2.1 Secondary Objective 1

The CIs for the single proportions will be calculated using the exact binomial method (Clopper-Pearson method, quoted by Newcombe (10), i.e., using the inverse of the beta integral with SAS[®]).

5.1.2.2.2 Secondary Objective 2

The proportions of subjects in a planned nonrandom subset (approximately 60 subjects from Group 1 and approximately 60 subjects from Group 2) with vaccine seroresponse for meningococcal serogroups A, C, W, and Y at 6 (window, 5–7) days following vaccination will be determined; 95% CIs of point estimates will be calculated assuming proportions follow a binomial distribution using the Exact method.

5.1.2.2.3 Secondary Objective 3

For GMTs, the 95% CIs of point estimates will be calculated using the normal approximation assuming antibody titers/concentrations are log normally distributed. For proportions, 95% CIs of point estimates will be calculated assuming proportions follow a binomial distribution using the Exact method.

Categorical variables will be summarized and presented by frequency counts, proportion percentages, and confidence intervals (CIs). The 95% CIs of point estimates will be calculated using the normal approximation for quantitative data and the exact binomial distribution (Clopper-Pearson method) for percentages (6).

RCDC figures and kinetic curves will be provided for the antibody titers against meningococcal serogroups contained in MenACYW conjugate vaccine.

Descriptive analyses on A, C, W, and Y serogroups will include:

- hSBA and rSBA GMTs and corresponding 95% CIs
- hSBA and rSBA titer distribution and RCDCs

- Percentages of subjects with hSBA titer $\geq 1:4$ and $\geq 1:8$ and corresponding 95% CIs
- Percentages of subjects with rSBA titer $\geq 1:8$ and $\geq 1:128$ and corresponding 95% CIs

